9.4 Sample Size

9.4.1 Phase 1 (Dose Escalation)

During the study, for the first 2 dose cohorts of the monotherapy, at least 2 subjects need to be evaluable. For the remaining cohorts, a minimum of 3 subjects evaluable for the DDS will be treated per dose cohort until determination of the MTD and/or one or more RP2Ds. At least 2 evaluable subjects are planned for the first 2 cohorts and at least 3 evaluable subjects per any following dose cohort thereafter. It is estimated that up to 41 subjects will be enrolled taking dropouts and additional subjects enrolled for some of the dose groups into account. The actual number of subjects will depend on the number of dose levels/cohorts that are tested.

9.4.2 Phase 2a (Dose Expansion)

An optimum Simon's two-stage design will be used for the expansion phase ([Simon 1989](#)). The assumptions and sample size calculations for different cohorts are summarized in [Table 10](#).

Table 10: Sample Size Consideration for Expansion Cohorts

Indication	Objective Response Rate		Interim Analysis		Final Analysis		One-sided test	
	Alternative hypothesis	Null hypothesis	Number of subjects	OR, that may lead to stop	Number of subjects*	OR (rejection of the null hypothesis)	Power	Type I error rate (α)

RAS wt, microsatellite stable CRC	25%	5%	11	≤ 1	39	≥ 4	80%	5%
ccRCC	30%	14%	15	≤ 2	41	≥ 10	81%	5%
NSCLC EGFRmut	30%	14%	15	≤ 2	41	≥ 10	81%	5%
Maximum number of subjects: 121								

ccRCC = clear cell renal cell carcinoma; CRC = colorectal cancer; EGFRmut = epidermal growth factor receptor mutant; NSCLC = non-small cell lung cancer; OR = objective response; RAS = rat sarcoma gene; wt = wild type.

*Up to a total of N~40 subjects per cohort according to the [FDA guideline, 2018](#)

In other words:

RAS wt,
microsatellite
stable CRC: The power that is computed at ORR=25% (alternative hypothesis) is 80%. If the treatment is actually not effective, there is a 0.05 (α) probability of concluding that it is. After testing the treatment on 11 subjects in the first stage, the study may be terminated if 1 or fewer responds. At final analysis (N=39) if the total number responding is less than or equal to 3, the treatment is rejected.

ccRCC: The power that is computed at ORR=30% (alternative hypothesis) is 81%. If the treatment is actually not effective, there is a 0.05 (α) probability of concluding that it is. After testing the treatment on 15 subjects in the first stage, the study may be terminated if 2 or fewer responds. At final analysis (N=41), if the total number responding is less than or equal to 9, the treatment is rejected.

NSCLC
EGFRmut: The power that is computed at ORR=30% (alternative hypothesis) is 81%. If the treatment is actually not effective, there is a 0.05 (α) probability of concluding that it is. After testing the treatment on 15 subjects in the first stage, the study may be terminated if 2 or fewer responds. At final analysis (N=41), if the total number responding is less than or equal to 9, the treatment is rejected.

The sample size is based on the safety analysis set for all subjects.

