9.3.8.2 Phase 2a (Dose Expansion)

An IA will be performed for each cohort independently, once the defined number of subjects (11, 15, and 15 subjects for Cohorts A, B, and C, respectively, – see [Table 10](#)) in the respective cohort have completed their first post-baseline assessment and its confirmation (2nd post-baseline assessment, ie, ≥ 12 weeks post-baseline) to be categorized under the primary response endpoint or have withdrawn from the study. Each cohort will be then assessed for futility. The results from this IA will be non-binding, unless no signs of efficacy are observed. Safety criteria will also be evaluated to decide on the continuation of the cohorts. During the conduct of the study, after the interim analysis for Cohort A and C and stopping these cohorts for futility, it was considered unlikely that the continuation criteria can be met in Cohort B. Hence it was decided to prematurely stop enrollment after 8 patients in Cohort B.

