4. SAMPLE SIZE AND POWER CALCULATION

Please refer to the protocol section 9.4 for sample size justifications.

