Primary endpoint for this phase will be Overall response rate (complete response [CR] + partial response [PR]) assessed by local RECIST v1.1. Best confirmed overall response will be used to define the ORR. The table below summarizes the confirmation rules:

Response at first visit	Response at consecutive visit (at least 4 weeks after the initial assessment)	Confirmed Response at visit
CR	CR	CR
CR	PR	PD
CR	SD	SD*
CR	PD	PD
PR	CR	PR
PR	PR	PR
PR	SD	SD*
PR	PD	PD
SD	CR	SD*

CONFIDENTIAL

Page 15 of 22

Statistical Analysis Plan template version 1.0 dated 27-MAR-2019

SD	PR	SD*
SD	SD	SD*
SD	PD	PD

CR = complete response; PD = progressive disease; PR = partial response; SD = stable disease

* - In order to assign Stable Disease as a confirmed response, there has to be another assessment of at least SD no less than 7 weeks after the initial visit. If this criterion is not satisfied, assign PD.

If the closest consecutive visit is closer than 4 weeks, or is not evaluable, use the next available assessment for confirmation. The last visit has no confirmed response. For iRECIST data similar approach will be used to define the confirmed response at visit.

Simon's two-stage design will be used to determine the outcome of the study in each of the three cohorts. The table below shows the decision thresholds for the design for all three cohorts:

Indication	Interim Analysis		Final Analysis	
	Number of subjects	OR, that may lead to stop	Number of subjects*	OR (rejection of the null hypothesis)
RAS-wt, microsatellite stable CRC	11	≤1	39	≥4
ccRCC	15	≤2	41	≥10
NSCLC EGFRmut	15	≤2	41	≥10

CRC = colorectal cancer; EGFRmut = epidermal growth factor receptor mutant; RAS-wt = rat sarcoma genes-wild type; NSCLC = non-small cell lung cancer; OR = objective response

*Up to a total of N~40 subjects per Cohort

The final analysis will take place after the last expansion arm was closed for futility or the last patient of the last expansion arm had the final end-of-study visit. Summaries will include the count and percentages of different best confirmed overall responses for each cancer type and observed ORR. In the final analysis, a p-value using the exact binomial test will be calculated comparing the response proportion to the probability stated under H_0 for each indication separately.

Listing of CT scan data, reporting both confirmed and unconfirmed responses at all visits will be created. Additionally, biopsy data will be listed.

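### The 81% power stated for the ccRCC and NSCLC cohorts does not reproduce: the printed two-stage rule has 76.8% power and an attained alpha of 4.4%

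*Protocol*

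**What the plan says.** Protocol section 9.4.2 introduces the design with "An optimum Simon's two-stage design will be used for the expansion phase". Table 10 gives the ccRCC and NSCLC rows identical entries: null 14%, alternative 30%, interim at 15 subjects with a possible stop at 2 or fewer responders, final analysis at 41 subjects with rejection of the null at 10 or more, power 81%, one-sided type I error 5%. The text under the table repeats this for each cohort: "The power that is computed at ORR=30% (alternative hypothesis) is 81" percent, and "After testing the treatment on 15 subjects in the first stage, the study may be terminated if 2 or fewer responds".

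The CRC row, used below as a check on method, has null 5%, alternative 25%, a possible stop at 1 or fewer in 11, and success at 4 or more in 39; its text says "The power that is computed at ORR=25% (alternative hypothesis) is 80" percent.

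On the status of the interim, Protocol section 9.3.8.2 says "The results from this IA will be non-binding, unless no signs of efficacy are observed", and SAP section 8 agrees. The synopsis calls the interim non-binding without that qualification.

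The SAP has no sample-size calculation of its own. Section 4 says "Please refer to the protocol section 9.4 for sample size justifications". Section 7.7.1 reprints the same stage sizes and cut-offs, introduced by "The table below shows the decision thresholds for the design for all three cohorts".

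**The concern.** Power and alpha of a two-stage binomial design follow exactly from six printed numbers: two response rates, two sample sizes and two cut-offs. For these two rows the printed power does not follow from the printed rule, and a 4-point gap is too large to be rounding.

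The stated power fixes how much weight a negative result carries. A reader who believes 81% takes the chance of missing a drug with a 30% response rate to be 19%; under the printed rule it is 23.2%. More than half of that (12.7 points) arises at the 15-patient interim, a figure that the plan does not give. The SAP takes its justification from the protocol by reference, so the error would pass into the study report for two of the three cohorts.

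**Working it through.** **Inputs** (Protocol Table 10 and its narrative; cut-offs confirmed in SAP section 7.7.1): p0 = 0.14, p1 = 0.30, n1 = 15, N = 41 (so 26 in stage 2), stop if x1 ≤ 2, success if the total is ≥ 10. No dropout adjustment is needed, because the sample size is based on the safety set.

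**Formula.** With the stop applied,

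P(success | p) = Σ over x1 = 3 to 15 of Bin(x1; 15, p) × P(Bin(26, p) ≥ 10 − x1).

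Power is this at p = 0.30 and alpha is this at p = 0.14.

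**Step 1: which convention does Table 10 use?** The CRC row (5% against 25%, 11 then 39 subjects, success at ≥ 4) is stated as 80% and 5%:

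| Stop rule, CRC | Power | Alpha |
|---|---|---|
| ≤ 1/11 applied | 80.2% | 4.8% |
| only at 0/11 | 95.4% | 10.1% |
| never | 99.4% | 12.9% |

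Only the first line matches. The CRC row was computed with the stop applied.

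**Step 2: the ccRCC and NSCLC rule at p = 0.30.**

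| x1 | P(x1) | P(enough in stage 2) | Product |
|---|---|---|---|
| 3 | 0.1700 | 0.7035 | 0.1196 |
| 4 | 0.2186 | 0.8374 | 0.1831 |
| 5 | 0.2061 | 0.9267 | 0.1910 |
| 6 | 0.1472 | 0.9740 | 0.1434 |
| 7 | 0.0811 | 0.9933 | 0.0806 |
| 8 | 0.0348 | 0.9989 | 0.0347 |
| 9 | 0.0116 | 0.9999 | 0.0116 |
| 10 to 15 | | 1 | 0.0037 |

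The products sum to **0.7677**. The same sum at p = 0.14 is **0.0444**. A simulation of 4 million trials gave 0.7676 and 0.0444.

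The chance of stopping at the interim is P(Bin(15, p) ≤ 2): 0.127 at p = 0.30 (0.0047 + 0.0305 + 0.0916, with rounding) and 0.648 at p = 0.14.

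Type II error is 1 − 0.768 = 23.2%, against the stated 1 − 0.81 = 19%, a difference of 4.2 points.

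**Step 3: does relaxing the stop recover 81% and 5%?**

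| Stop rule, ccRCC and NSCLC | Power | Alpha |
|---|---|---|
| ≤ 2/15 (printed) | 76.8% | 4.44% |
| ≤ 1/15 | 81.7% | 5.08% |
| only at 0/15 | 82.8% | 5.25% |
| never | 83.0% | 5.27% |

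None gives 81% with alpha at or below 5%. Going through every fixed pair of interim and final cut-offs with 15 then 41 subjects, the highest power with alpha at or below 5% is 76.8%, at the printed pair; the next best is 72.5% (no stop, success at ≥ 11). A discretionary policy could average the stated figures. Stopping at 0 or 1 and continuing at exactly 2/15 with probability 0.86 gives 0.86 × 0.8171 + 0.14 × 0.7677 = 0.810 and 0.86 × 0.0508 + 0.14 × 0.0444 = 0.0499. The plan specifies no such policy.

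**Step 4: changing the final cut-off, stop applied.** Success at ≥ 9 gives 82.3% power with alpha 8.7%; success at ≥ 11 gives 68.3% with alpha 2.0%. Neither matches.

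**The case against.** The strongest defence is that the interim is non-binding, so the 81% need not assume that the stop is applied. It fails on two counts. The adjacent CRC row, under the same interim policy, reproduces only with the stop applied. And dropping the stop for ccRCC and NSCLC gives 83.0%, not 81%, with alpha 5.27%, above the stated 5%. The nearest relaxed rule, stopping at 1 or fewer in 15, gives 81.7% and 5.08% and contradicts the printed cut-off.

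A second objection has more force: the power may be right and the interim rule mis-stated. Keeping 41 subjects and success at 10 or more, stopping at ≤ 1/14 gives 81.05% and 4.996%, ≤ 2/18 gives 80.9% and 4.94%, and ≤ 3/22 gives 81.0% and 4.93%. The documents cannot say whether one of these was intended. But 15 subjects with a cut-off of 2 is what Table 10, both narratives and SAP section 7.7.1 print, so the stated power is wrong for the rule in the plan. The possibility is a reason to check the source calculation.

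Third, 5% can be read as a nominal ceiling, which 4.4% respects; the CRC row likewise attains 4.8% and is printed as 5%. That stands: with the stop applied, type I error is not inflated, and the error is in the power.

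Finally, the practical weight is limited. Cohort C was stopped for futility and Cohort B closed after 8 patients, before its interim, so neither will reach the 41-patient analysis. For Cohort C the figure that bears most on interpretation is the 12.7% interim false-stop probability.

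**Conclusion.** The point holds. For the rule as printed with the stop applied, power at a 30% response rate is 76.8% rather than 81%, type II error is 23.2% rather than 19%, attained alpha is 4.4%, and the chance of stopping an effective drug at the interim is 12.7%. Across the discretion that a non-binding interim leaves, power runs from 76.8% to 83.0% and alpha from 4.4% to 5.3%. All inputs are printed in the protocol and the calculation is exact; the only assumption is independent responses with a common rate, which the design itself makes. What cannot be settled from the documents is whether the power or some other entry was mis-transcribed. The error misstates the design properties of two of the three cohorts, but no pending enrolment decision depends on it.

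**What to change.** In Table 10 (ccRCC and NSCLC rows) and the two matching narrative paragraphs of Protocol section 9.4.2:

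- state power as about 77% and attained alpha as about 4.4%, with the futility stop at ≤ 2/15 enforced;
- add that the probability of stopping at the interim is 12.7% when the true response rate is 30%;
- add that, because the interim is non-binding, power can reach 83.0% with alpha 5.3% if the stop is not applied (82.8% and 5.25% if the trial stops only at 0/15).

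Check the source calculation for a mis-transcribed input or cut-off, without presuming which, and carry the reconciled figures into the study report. If attained alpha is shown for these rows, show the CRC row on the same basis (80.2% power, 4.8% alpha, 19.7% chance of an interim stop at a true 25%), so that the table does not mix attained and nominal values.

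The cost is a wording change to one table and its text; the SAP follows by reference. No patients are added and no threshold changes. The stated power becomes slightly less favourable.

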10.0 QUALITY CONTROL AND QUALITY ASSURANCE

10.1 Data Recording, Monitoring of the Study, and Regulatory Compliance

The project manager, or their designee, will make an initiation site visit to each institution to review the protocol and its requirements with the Investigator(s), inspect the drug storage area, fully inform the Investigator of his/her responsibilities and the procedures for assuring adequate and correct documentation. During the initiation site visit, the eCRF and other pertinent study materials will be reviewed with the Investigator's research staff. During the study, the CRA will make regular site visits in order to review protocol compliance, examine CRFs and individual subject's medical records, and assure that the study is being conducted according to pertinent regulatory requirements including ICH-Good Clinical Practice (GCP). Sites should ensure that source documentation is available to enable verification of all eCRF data entries. The review of medical records will be done in a manner to ensure that subject confidentiality is maintained.

All eCRF data will be collected using an eCRF within a fully validated and CFR 21 Part 11-compliant electronic data capture system. All data will be entered into the eCRF by the site staff. These data will then be source-data verified and reviewed by the CRAs before data cleaning by Data Management is performed. All queries will be raised and resolved within the electronic data capture system. During entry, programmatic checking of the data will be performed and once saved into the database, more complex programmatic checks will also be performed. During the conduct of the study, all system users will have real-time access to the data. The level of access to the data and study privileges will be determined by their user role.

After all queries have been resolved, the Statistical Analysis Plan approved and signed, and any summary/analysis populations approved, the database will be locked, and the data released for summary and analysis. All summary and analysis of the data will be performed using appropriate versions of SAS® and WinNonLin Pro, or equivalent.

10.2 Study Monitoring

Clinical research associates will be responsible for the monitoring of the study. The CRA will review the progress of the study on a regular basis to ensure adequate and accurate data collections. Monitoring site visits to review the eCRF, subject case notes, administrative documentation including the Investigator Site File, and frequent telephone/e-mail communications with the site will be performed throughout the study.

At each study monitoring visit, the Investigator will make available all records pertaining to the study. To allow sufficient time to assemble documentation for the CRA, monitoring visits will be confirmed in advance of planned visits.

The process for study monitoring and source data verification requirements for the study will be specified in the Monitoring Plan (or equivalent).

10.3 Clinical Study Audit

The Sponsor, Sponsor representative, or external regulatory agency may at any time during or after completion of the study conduct a GCP audit. Prior notice will be given to each site selected for audit in advance of a planned audit.

10.4 Clinical Study Report

The results of the study will be presented in an integrated CSR according to ICH guidelines. The CSR will be written once all expansion cohorts reach the primary endpoint assessment (see Section 9.3.4.2).

In case subjects are still being treated with study medication at the primary analysis cut-off date for this study, such subjects will be kept on treatment in the study and data collected will then be reported in an addendum to the final CSR. It will be noted in the final CSR that such a revised report may be provided.

10.5 Data Availability

The Investigator is required to maintain copies of all essential study documentation, including the Site Study File, all eCRF data (including the full audit trail and all data queries), signed ICFs, and records for the receipt and disposition of study drug.

During the study, the Investigator must make study data accessible to the CRA, the Sponsor (or a third-party auditor assigned by the Sponsor), and relevant IRB/EC and regulatory agencies. A file (or appropriate records) for each subject must be maintained that includes the signed ICF and all source documentation related to that subject. The Investigator must ensure the availability of source documents from which the information in the eCRF was derived.

Please refer to Section 12.2 for details of required record retention for the study.

10.6 Curricula Vitae and Financial Disclosure of Investigators

All Principal Investigators will be required to provide a current signed and dated curriculum vitae, a completed FDA Form 1572 (or accepted equivalent) and a financial disclosure statement. All Sub-Investigators will be required to provide a current curriculum vitae and a financial disclosure statement.

10.7 Protocol Modifications

No modification of the protocol should be implemented without the prior written approval of the Sponsor. Any such changes which may affect a subject's treatment or informed consent, especially those increasing potential risks, must receive prior approval by the IRB/EC. The exception to this is where modifications are necessary to eliminate an immediate hazard to study subjects, or when the change involves only logistical or administrative aspects of the study (e.g., change in monitor, change in telephone number). Other administrative revisions which may impact the clinical portion of a study will be duly reported to the IRB/EC by the Principal Investigator.

10.8 Study or Site Termination

If the Sponsor or their representatives, Investigator, or Competent Authority discover conditions during the study that indicate that the study or site involvement should be terminated, this action may be taken after appropriate consultation with the Sponsor and the Investigator. Conditions that may warrant termination of the study or a study site include, but are not limited to:

- The discovery of an unexpected, serious, or unacceptable risk to subjects enrolled in the study;
- The decision on the part of the Sponsor to suspend or discontinue testing, evaluation, or development of the study drug;
- Failure of an Investigator(s) to comply with pertinent clinical study regulations;
- Submission of knowingly false information from the study site to the Sponsor, CRA, or Competent Authority; and
- Insufficient adherence to protocol requirements.
- Study termination and/or site close out will be performed in accordance with applicable local regulations.

11.0 ETHICAL CONSIDERATIONS

The Investigator will obtain written informed consent from each subject, or their authorized representative, participating in the study. The ICF must be signed, witnessed, and dated. The ICF will contain all the Essential Elements of Informed Consent set forth in 21 CFR, Part 50, the ICH Guideline for GCP, and the terms of the Declaration of Helsinki. Copies of the signed document should be given to the subject and filed in the Investigator's Study File, as well as the subject's medical record if in conformance with the institution's standard operating procedures.

The final study protocol and subject ICF will be approved by the appropriate IRB/EC for each investigational site. Approval will be received in writing before initiation of the study.

Changes to the protocol during the study will be documented as amendments. Depending on the contents of the amendment and local legal requirements, the amendment will be submitted for approval to the relevant IRB/EC and to the relevant competent authorities prior to implementation. Exceptions are cases of changes made to protect subject safety, which will be implemented immediately.

If an amendment substantially alters the study design, increases the potential risk to the subjects, affects the treatment of the subject, or might otherwise influence the willingness of the subject to participate in the study, then the ICF must be revised and submitted to the relevant IRB/EC and, where necessary, to the relevant competent authorities, for review and approval. When a subject is currently undergoing study procedures and is affected by the amendment, then the subject must be asked to consent again using the new ICF.

11.1 Ethical Conduct of the Study

The study will be conducted in accordance with ICH GCP, the Declaration of Helsinki, the European Union Clinical Trials Directive 2001/20/EC, the GCP Directive 2005/28/EC, the requirements of local IRB/EC, and the US Code of Federal Regulations, Title 21 CFR Part 50.

11.2 Informed Consent

The principles of informed consent in the Declaration of Helsinki and GCP guidelines will be implemented before any protocol-specific procedures or interventions are carried out.

All subjects will be informed that participation is voluntary and that they can cease participation at any time without necessarily giving a reason and without any penalty or loss of benefits to which they are entitled.

With the help of the ICF, the subject will be informed about the AFM24 study drug and anticipated effects and the reason, design, and implication of the study. The subject must give consent to participate prior to enrollment in the study. This consent must be given in writing. The Investigator who conducts the informed consent discussion must also sign the ICF. The Investigator may delegate this responsibility to a suitably qualified member of the study team (eg, Sub-Investigator) if permitted by local regulations. This delegation of responsibility must be recorded in the Study File. By giving signed consent, the subject will confirm that his or her participation is voluntary and that he or she will follow the instructions of the Investigator and answer the questions asked. Signatures must be personally dated.

The signed and dated consent form will be kept by the Investigator. Prior to participation in the study, the subject should receive a copy of the signed and dated written ICF.

The ICF must include all elements required by law, local regulations, GCP guidelines, and ICH guidelines, including consent to allow the Sponsor, Sponsor representative, or external regulatory auditor to review the subject's medical records. This gives permission to examine, analyze, verify, and reproduce any records and reports that are important to the evaluation of the study.

Any party with direct access must take all reasonable precautions within the constraints of the applicable regulatory requirement(s) to maintain the confidentiality of the subjects' identities and Sponsor's proprietary information. It is the CRA's responsibility to verify that each subject has consented, in writing, to direct access.

